To compare the efficacy and health-related quality of life of twice-daily topical application of delgocitinib cream with once-daily oral administration of alitretinoin capsules in the treatment of patients with severe CHE.	 Efficacy: IGA-CHE TS at Week 24. HECSI-75 at Week 12 and Week 24. HECSI-90 at Week 24. Change in HESD itch score (weekly average) from baseline to Week 24. Reduction of HESD itch score (weekly average) of ≥3 points ¹ at Week 12 and Week 24 AUC from baseline to Week 24 of reduction of HESD 				

Objectives	Endpoints
	itch score (weekly average) of ≥3 points ¹ .
	• Reduction of HESD itch score (weekly average) of ≥4 points ² at Week 12 and Week 24
	• AUC from baseline to Week 24 of reduction of HESD itch score (weekly average) of ≥4 points ² .
	Change in HESD pain score (weekly average) from baseline to Week 24.
	• Reduction of HESD pain score (weekly average) of ≥3 points ³ at Week 12 and Week 24.
	• AUC from baseline to Week 24 of reduction of HESD pain score (weekly average) of ≥3 points ³ .
	• Reduction of HESD pain score (weekly average) of ≥4 points ⁴ at Week 12 and Week 24.
	AUC from baseline to Week 24 of reduction of HESD pain score (weekly average) of ≥4 points ⁴ .
	Change in HESD score (weekly average) from baseline to Week 12 and Week 24.
	 Reduction of HESD score (weekly average) of ≥3 points ⁵ at Week 12 and Week 24.
	 Reduction of HESD score (weekly average) of ≥4 points ⁶ at Week 12 and Week 24.
	Health-related quality of life:
	Change in DLQI score from baseline to Week 12 and Week 24.
	• Reduction of DLQI score of ≥4 points ⁷ at Week 12 and Week 24.
	DLQI score of 0 or 1 at Week 12 and Week 24.
	Change in HEIS (individual domains and total score) from baseline to Week 12 and Week 24.
	Change in EQ-5D-5L index score from baseline to Week 12 and Week 24.
	Change in EQ-5D-5L visual analogue scale score from baseline to Week 12 and Week 24.
To evaluate the effect of twice-daily topical	TSQM at Week 12 and at Week 24.
application of delgocitinib cream on treatment satisfaction and work productivity compared with once-daily oral administration of alitretinoin capsules in the treatment of patients with severe CHE.	Change in WPAI-CHE (each individual domain) score from baseline to Week 12 and Week 24 ⁸ .
To compare the safety of twice-daily topical application of delgocitinib cream with once-daily	• Number of events of increased levels of triglycerides >3.42 mmol/L (fasted state) up to Week 26.

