oral administration of alitretinoin capsules in the treatment of patients with severe CHE.	Number of AEs of hypertriglyceridaemia up to Week 26.
	• Number of events of increased levels of cholesterol >7.75 mmol/L (fasted state) up to Week 26.
	Number of AEs of hypercholesterolaemia up to Week 26.
	Number of AEs of headache up to Week 26.

Objectives	Endpoints
	Number of AEs of liver toxicity up to Week 26.
	• Number of events of increased levels of ALT and/or AST >3×ULN (or >3×baseline if baseline was abnormal but <2×ULN) up to Week 26.
	• Number of events of increased levels of ALP >2.5×ULN up to Week 26.
	• Number of events of increased levels of bilirubin >1.5×ULN up to Week 26.

- 1. Among participants with a baseline HESD itch score (weekly average) ≥3 points.
- 2. Among participants with a baseline HESD itch score (weekly average) ≥4 points.
- 3. Among participants with a baseline HESD pain score (weekly average) ≥ 3 points.
- 4. Among participants with a baseline HESD pain score (weekly average) ≥4 points.
- 5. Among participants with a baseline HESD score (weekly average) \geq 3 points.
- 6. Among participants with a baseline HESD score (weekly average) ≥4 points.
- 7. Among participants with a baseline DLQI score ≥4 points.
- 8. Among participants with paid work at baseline.

Abbreviations: AE=adverse event; ALT=alanine aminotransferase; AST=aspartate aminotransferase; AUC=area under the curve; CHE=chronic hand eczema; DLQI=Dermatology Life Quality Index; EQ-5D-5L=EuroQol 5-Dimension Health Questionnaire 5 Level; HECSI=Hand Eczema Severity Index; HECSI-75=at least 75% improvement in HECSI score from baseline; HECSI-90=at least 90% improvement in HECSI score from baseline; HEIS=Hand Eczema Impact Scale©; HESD=Hand Eczema Symptom Diary©; IGA-CHE=Investigator's Global Assessment for chronic hand eczema©; IGA-CHE TS=IGA-CHE treatment success; SAE=serious adverse event; TSQM=Treatment Satisfaction Questionnaire for Medicine; ULN=upper limit of normal; WPAI-CHE=Work Productivity and Activity Impairment – Chronic Hand Eczema.

4 Trial Design

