5.1 Inclusion Criteria

Participants are eligible to be included in the trial only if all of the following criteria apply:

Age

1. Participant must be at least 18 years of age inclusive, at the time of signing the informed consent.

Type of Participant and Disease Characteristics

- 2. Diagnosis of CHE defined as hand eczema that has persisted for more than 3 months or returned twice or more within the last 12 months.
- 3. Disease severity graded as severe at screening and baseline according to IGA-CHE (i.e. an IGA-CHE score of 4).
- 4. Documented recent history of inadequate response to treatment with TCS (at any time within 1 year before the screening visit) or for whom TCS are documented to be otherwise medically inadvisable (e.g. due to important side effects or safety risks).

- a. Inadequate response is defined as a history of failure to achieve and maintain a low disease activity state (comparable to an IGA-CHE score ≤2) despite treatment with a daily regimen of TCS of III-IV (potent to very potent) for the European Union (EU) and IV-I (medium potency to very/ultra-high potency) for Canada, applied for at least 28 days or for the maximum duration recommended by the product prescribing information, whichever is shorter.
- b. Important side effects or safety risks are those that outweigh the potential treatment benefits and include intolerance to treatment, hypersensitivity reactions, and significant skin atrophy as assessed by the physician.
- 5. Participant is adherent to standard non-medicated skin care including avoidance of known and relevant irritants and allergens.

Contraceptive/Barrier Requirements

6. Contraceptive use must be consistent with local regulations (if they are stricter than the protocol requirements) regarding the methods of contraception for those participating in clinical studies.

For female participants:

- A female participant is eligible to participate if she is not pregnant (see Appendix 4), not breastfeeding, and 1 of the following conditions applies:
 - o Not a WOCBP as defined in Appendix 4.

OR

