8.1.3.2 Dermatology Life Quality Index (DLQI)

The DLQI is a validated questionnaire with content specific to those with dermatologic conditions. It consists of 10 items addressing the participant's perception of the impact of their skin disease on different aspects of their quality of life over the last week, such as dermatology-related symptoms and feelings, daily activities, leisure, work or school, personal relationships, and the treatment (Finlay et al, 1994). Each item is scored on a 4-point Likert scale (0='not at all/not relevant'; 1='a little'; 2='a lot'; 3='very much'). The DLQI score is the sum of the 10 items (score ranging from 0 to 30); a high score is indicative of a poor quality of life.

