9.2 Analysis Sets

For purposes of analysis, the following analysis sets are defined:

Table 9-1 Participant Analysis Sets

Participant Analysis Set	Description
Full analysis set	All randomised participants. Participants will be included in the analyses according to randomised treatment allocation. Exclusions from the FAS can be considered in special cases, as described in Section 5.2.1 (Full Analysis Set) of ICH E9 guidelines. If a participant is excluded from the FAS, a justification per ICH E9 guidelines will be given.
Safety analysis set	All participants who are exposed to the IMP. Participants will be analysed according to the treatment they actually received.

Abbreviations: FAS=full analysis set; IMP=investigational medicinal product.

The full analysis set (FAS) is used to analyse endpoints related to the efficacy objectives and the safety analysis set is used to analyse the endpoints and assessments related to safety.

The decisions regarding inclusion/exclusion of participants or participant data from the analysis sets will be documented in the analysis set definition document before DBL.

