9.3.6 Estimand Strategy

9.3.6.1 General Considerations

The analysis of endpoints related to efficacy and health-related quality of life will be based on the FAS.

The following primary and supplementary estimands will be defined for binary, continuous, and AUC endpoints (primary and key secondary endpoints):

- The primary estimand will use a 'composite' strategy to handle IEs. With a 'composite' strategy, the occurrence of an IEs is a component of the endpoint. The occurrence of any IE will lead to assume failure of the randomised treatment. For continuous endpoints, observed data after the IEs will be imputed as non-response by using WOCF (including baseline value) which is considered an extremely unfavourable value.
- A first supplementary estimand will use a 'pandemic modified composite' strategy. The strategy follows a 'composite' strategy for IEs independent of the COVID-19 pandemic. However, data collected after the IE related to the COVID-19 pandemic will be 'treated as missing' and imputed assuming MAR.
- A second supplementary estimand will use a 'treatment policy' strategy which attempts to quantify the effect of the randomised treatment, ignoring the occurrence of IEs. This policy reflects the intention-to-treat (ITT) principle and is intended to measure the effectiveness of the treatment under conditions closer to 'real world' conditions where patients will not adhere perfectly to the protocol when taking medication. Data collected for the endpoint of interest are used regardless of whether an IE occurred, except for the occurrence permanent discontinuation of IMP related to the COVID-19 pandemic data which will be assumed MAR and imputed.

To support the 'treatment policy' strategy, participants who experience IEs prior to Week 12 will be asked to attend the primary endpoint visit at Week 12 and nominal visit at Week 24 for collection of data. Participants who experience IEs between Week 12 and Week 24 will be asked to attend the nominal visit at Week 24 for collection of data.

For primary and key secondary endpoints only, pre-specified sensitivity analyses will also be conducted for selected combinations of endpoints and estimands to assess the robustness of the results with respect to the handling of missing data.

Analysis to summarise and assess the effect of patterns of missing data related to the COVID-19 pandemic will be specified in the SAP prior to DBL.

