9.3.6.3 Estimand Strategy for Binary Endpoints

The population level summary will be the difference in response rates between delgocitinib cream and alitretinoin capsules.

The difference in response rates between the 2 treatment groups with the 95% CI will be calculated using the Cochran-Mantel-Haenszel (CMH) test stratified by region and hyperkeratotic/non-hyperkeratotic subtype.

When analyses require MI procedures of data, 100 complete datasets will be sampled. For each dataset, the difference in response rates will be analysed using the CMH test stratified by region and hyperkeratotic/non-hyperkeratotic subtype. The results of the analyses will be combined using Rubin's rule to provide the estimated treatment difference and associated standard error, and the 95% CI for the treatment difference will be calculated.

Primary Estimand: 'Composite' Strategy

For the primary analysis, observed data and missing data will be handled according to the IEs, as described in Table 9-2.

For the sensitivity analysis, which is rather conservative against the delgocitinib group, missing data at the endpoint of interest for participants who did not experience IEs prior to that will be handled as follows:

- For participants in the delgocitinib cream group, missing data will be imputed as non-response.
- For participants in the alitretinoin capsules group, missing data will be imputed using MI (100 iterations) assuming MAR. Binary response/non-response will be determined after imputation of the original raw continuous values when binary variable is obtained by derivation (e.g. for the HECSI-90 from baseline up to Week 24, the percentage of reduction from baseline will be derived from imputed values).

First Supplementary Estimand: 'Pandemic Modified Composite' Strategy

Observed data and missing data will be handled according to the IEs, as described in Table 9-2.

All missing or 'treated as missing' data will be imputed using MI assuming MAR within treatment groups. Once the 100 complete data sets have been generated by MI, non-responder imputation of relevant data points not affected by the COVID-19 pandemic will be applied.

Second Supplementary Estimand: 'Treatment Policy' Strategy

For the primary analysis, observed data and missing data will be handled according to the IEs, as described in Table 9-2.

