9.3.9 Exploratory Endpoints Analysis

The analysis of exploratory endpoints will be based on the FAS.

The analysis of exploratory endpoints will resemble the primary analysis for the primary estimand related to a specific endpoint type: binary, continuous, or AUC. For details refer to Section 9.3.6.

Table 9-4 provides an overview of the statistical analysis of the exploratory endpoints.

Table 9-4 Overview of the Statistical Analysis of Exploratory Endpoints

Endpoints	Type of	Primary estimand					
	endpoint	Strategy to handle IEs	Handling of missing data and data collected after IE				
Effica	асу						
IGA-CHE TS at Week 24.	Binary	Composite	Non-response imputation				
HECSI-75 at Week 12 and Week 24.							
HECSI-90 at Week 24.							
Reduction of HESD itch score (weekly average) of ≥3 points ¹ at Week 12 and Week 24.							
Reduction of HESD itch score (weekly average) of ≥4 points ² at Week 12 and Week 24.							
Reduction of HESD pain score (weekly average) of \geq 3 points ³ at Week 12 and Week 24.							
Reduction of HESD pain score (weekly average) of ≥4 points ⁴ at Week 12 and Week 24.							
Reduction of HESD score (weekly average) of ≥3 points ⁵ at Week 12 and Week 24.							
Reduction of HESD score (weekly average) of ≥4 points ⁶ at Week 12 and Week 24.							
Change in HESD itch score (weekly average) from baseline to Week 24.	Continuous	Composite	WOCF (including baseline value)				
Change in HESD pain score (weekly average) from baseline to Week 24.							
Change in HESD score (weekly average) from baseline to Week 12 and Week 24.							
AUC from baseline to Week 24 of reduction of HESD itch score (weekly average) of ≥3 points ¹	AUC (derived	Composite	Non-response imputation				
AUC from baseline to Week 24 of reduction of HESD itch score (weekly average) of ≥4 points ²	from binary)						
AUC from baseline to Week 24 of reduction of HESD pain score (weekly average) of ≥3 points ³							
AUC from baseline to Week 24 of reduction of HESD pain score (weekly average) of ≥4 points ⁴							
Health-related quality of life							
Change in DLQI score from baseline to Week 12 and Week 24.	Continuous	Composite	WOCF (including baseline value)				
Change in HEIS (individual domains and total score) from baseline to Week 12 and Week 24.							
Change in EQ-5D-5L index score from baseline to Week 12 and Week 24.							
Change in EQ-5D-5L visual analogue scale score from baseline to Week 12 and Week 24.							

Endpoints	Type of	Primary estimand		

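### The exploratory endpoint DLQI 0 or 1 has no baseline DLQI condition, so a participant who starts and stays at 0 or 1 counts as a responder without improving

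*Combined protocol and SAP*

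**What the plan says.** Section 3, Table 3-2, lists "DLQI score of 0 or 1 at Week 12 and Week 24" among the exploratory quality-of-life endpoints, with no footnote marker. Table 9-4 in Section 9.3.9 repeats it as a binary endpoint under the composite strategy with non-response imputation, again without a marker. The DLQI endpoint listed beside it, a reduction of at least 4 points, carries footnote 7: "Among participants with a baseline DLQI score ≥4 points".

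Entry severity is set by the investigator's scale alone (Section 5.1, criterion 3): "Disease severity graded as severe at screening and baseline according to IGA-CHE (i.e. an IGA-CHE score of 4". Neither Section 5.1 nor Section 5.2 mentions DLQI, and the Schedule of Activities first collects it at the baseline visit. Section 8.1.3.2 gives the scale: "The DLQI score is the sum of the 10 items (score ranging from 0 to 30"; a baseline of 0 or 1 is therefore a possible value.

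On the population, Section 9.3.9 states "The analysis of exploratory endpoints will be based on the FAS", and Table 9-1 defines that set as "All randomised participants. Participants will be included in the analyses according to randomised treatment allocation". Section 9.3.6.3 analyses binary endpoints with a "Cochran-Mantel-Haenszel (CMH) test stratified by region and hyperkeratotic/non-hyperkeratotic subtype", which has no baseline DLQI term. Under the composite strategy (Section 9.3.6.1), "The occurrence of any IE will lead to assume failure of the randomised treatment", and Table 9-2 sets missing values to non-response.

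**The concern.** The endpoint is an absolute state measured after treatment. For a participant who starts above 1, reaching it requires improvement. For one who starts at 0 or 1 it does not: going from 1 to 1 is a response, and so is worsening from 0 to 1. Eligibility does not rule such participants out, the analysis set keeps them, and the test does not adjust for where they started.

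IGA-CHE treatment success, the plan's other 0-or-1 endpoint, avoids this in two ways: entry requires a score of 4, and the definition also asks for a drop of at least two steps. DLQI 0 or 1 has neither safeguard.

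At stake is how one exploratory quality-of-life result reads. Both response rates would include some people who had no measurable impairment to lose, and the difference between arms would look a little smaller than it is among those who could improve.

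**Working it through.** **The plan's own figure.** The documents give no response rate, power or baseline distribution for this endpoint. The only sample-size figure is for the primary endpoint (Section 9.5: difference 7.5, SD 30, 255 per arm, 1-sided 2.5%, 80% power). It reproduces: 7.5 / (30 × √(2/255)) = 2.823; 2.823 − 1.960 = 0.863; power = Φ(0.863) = 80.6%. Nothing below depends on it.

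**Formula.** Let f be the share at baseline DLQI 0 or 1, r the probability that they are again at 0 or 1 at the visit with no intercurrent event or missing value, and pD and pA the response rates among everyone else.

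- Observed rate in an arm: f·r + (1 − f)·p. This exceeds p by f·(r − p), so the rate rises whenever r is above p.
- Observed difference: (1 − f)·(pD − pA) + f·(rD − rA). If r is the same in both arms, the second term vanishes and the difference shrinks by exactly the share f, whatever r is.

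**Illustration.** Assumptions, not document figures: pD = 40%, pA = 28%, r = 100% in both arms, 255 per arm before any restriction, 1-sided 2.5%.

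| Share f | Number per arm (255·f) | Observed rates | Difference, all randomised | Power, all randomised | Power, baseline ≥2 only (true difference 12.0) |
|---|---|---|---|---|---|
| 1% | 2.6 | 40.6% vs 28.7% | 11.9 points | 80.7% | 81.4% |
| 2% | 5.1 | 41.2% vs 29.4% | 11.8 points | 79.5% | 81.0% |
| 5% | 12.8 | 43.0% vs 31.6% | 11.4 points | 76.0% | 79.8% |
| 10% | 25.5 | 46.0% vs 35.2% | 10.8 points | 70.1% | 77.6% |

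For f = 5%, delgocitinib is 0.05 × 1 + 0.95 × 0.40 = 43.0%, alitretinoin is 0.05 × 1 + 0.95 × 0.28 = 31.6%, and the difference is 0.95 × 12.0 = 11.4 points. With r = 80% the differences are the same and unrestricted power at f = 5% is 76.5%. Restricting recovers power even though it drops participants.

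**How large f might be.** The documents are silent, so this is a range under assumptions: true DLQI with mean 9 to 13 and SD 6 to 7, normal visit error giving a visit-to-visit difference SD of 2 to 4, rounded and held to 0–30, with no treatment effect. Baseline and Week 12 then have the same distribution, so the share at baseline 0 or 1 equals the no-effect response rate. The lower tail depends heavily on the assumed shape:

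| Shape | Share at 0 or 1 (mean 12, SD 7, difference SD 3) |
|---|---|
| Scaled beta on 0–30 | about 6.0% |
| Gamma | about 3.0% |
| Lognormal | about 1.5% |

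Over all settings and shapes the range is about 0.3% to 12%. A beta shape alone gives about 3.4% to 12%, so that lower end comes from the choice of shape.

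**Retention.** In the central beta case only about 42% of those at baseline 0 or 1 are at 0 or 1 again at Week 12, before any composite failure is counted. Limiting to baseline 2 or more lowers the no-effect rate there from about 6.0% to 3.6%.

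**The case against.** The strongest reply is that an absolute state is a legitimate endpoint. The proportion of all randomised participants with little or no impact at Week 12 or 24 is coherent as a description, and restricting it changes the population. Improvement itself is covered elsewhere: change in DLQI is analysed with baseline as a covariate, the 4-point reduction has its own baseline limit, and the AUC of DLQI change is a key secondary endpoint. This stands as a reason to keep the all-randomised figure as supplementary. It does not remove the fact that the comparison includes people who can respond without improving.

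A reader might infer that footnotes 1 to 7 set a rule which this endpoint breaks. They do not. A 4-point fall is arithmetically impossible from a baseline below 4, so those footnotes remove certain non-responders; here a low baseline makes response possible without change. The footnotes show only that the sponsor allowed for low baseline scores.

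A reader might also infer that everyone at baseline 0 or 1 is automatically a responder. That is not supported either: the score must still be 0 or 1 at the visit, and rescue treatment, permanent discontinuation of trial medication or a missing value makes the participant a non-responder.

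Finally, few participants may be affected. All have IGA-CHE 4 and either documented inadequate response to topical corticosteroids or a documented reason not to use them, and a DLQI of 1 means one item out of ten scored at its lowest positive level. That is plausible, but the documents give no figure. Section 9 also defers detail to a separate SAP whose text is not in the combined document, so a restriction there cannot be ruled out.

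**Conclusion.** The omission is real and minor. As written, a participant at DLQI 0 or 1 at baseline who remains there, without an intercurrent event or missing value, is a responder. The difference shrinks by about the share of such participants, provided they keep that score equally often in both arms. Both rates rise if these participants respond more often than the rest. The share is unknown, with an assumed range of about 0.3% to 12%; the power figures rest on assumed rates of 40% and 28%.

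Stronger conclusions are not supported. A reader might infer bias towards one treatment, but randomisation balances baseline DLQI in expectation, so what remains is dilution plus chance imbalance. Nor is the confirmatory result at risk: the endpoint is exploratory and outside the testing sequence of Section 9.1.1, so type I error and the primary and key secondary conclusions are unaffected. Nor is there a case here that the endpoint needs a minimum change or a confirmatory visit: a move from 2 to 1 would still count after the fix below, and that is acceptable for an absolute-state endpoint.

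**What to change.** Add a footnote to this endpoint in Tables 3-2 and 9-4 limiting it to participants with a baseline DLQI score of 2 or more, worded like footnotes 1 to 7. Report the number at baseline 0 or 1 by arm. The baseline summaries in Sections 9.3.1 and 9.3.4 would give means, quartiles and extremes of DLQI, but not necessarily that count. Keep the all-randomised result as a supplementary analysis.

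The restriction uses a value from the baseline visit, already collected, so it does not compromise the randomised comparison. The cost is one footnote, one extra count and a small share of participants leaving the denominator of one exploratory endpoint. Making the change before database lock avoids a later choice between two results.
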